3.3 Data Source/Data Collection Process

Data sources

As part of this feasibility study, we will explore the most appropriate mechanism to identify patients who have experienced recent minor and major bleeds. We will extend recruitment across both primary and secondary care, including wards and the ED. Patients attending anticoagulation clinics at the Swansea City Health Cluster (made up of eight separate general practices) will be identified by the practice pharmacist or nurse. They will be given information about the study and will consent for a research nurse to contact them to complete the study questionnaires. Research nurses based in Swansea University's Joint Clinical Research Facility (JCRC) will undertake regular exploration of Morriston Ward F audit data (Stroke ward) to identify patients who have experienced a recent bleed. Our GP investigator will also identify patients from ED records at Morriston hospital. Lastly, e-cards will be sent to specific patient groups on forums, social media, web site and newsletters, which are run by online AF support networks.

Outcomes

Quality of life and the impact of the anticoagulation treatment will be collected via validated patient-reported outcome measures (PROMs). We will also include a small number of additional relevant questions regarding when the bleed occurred, the nature of the bleed, and current treatment for the patient. We will also collect the documented cause and location of bleed as identified in discharge summary (for secondary care) in patients with major bleeds. Patient reported bleeds will be posthumously classified into minor or major bleeds by a clinician.

Exposure

Oral anticoagulant to prevent stroke following diagnosis of AF.

Data collection

Cases will be identified from i) routine anticoagulation clinics in primary care, ii) from hospital records for ward patients and from ED records. QoL data will be collected directly from patients via questionnaires. We envisage that data will be collected from patients via an electronic tool, ideally via patients' phones or tablets. We will also produce paper versions of questionnaires for patients who do not have access to a smartphone/tablet or would prefer this method of questionnaire completion. In order to maximise data collection, we will collect data directly from patients attending primary or secondary care if feasible or by phone or post.

A subset of patients with AF will also be invited to participate in structured interviews in order to capture emotive data and to draw out any common themes in issues relating to burden of side effects, specifically higher bleeding risks, from anticoagulants. Interview questions have been informed by public and patient representatives who have close experience with those who have AF or live with the condition themselves. Additionally, questions have been designed with input from relevant clinical staff, including a consultant hematologist. In order to limit any potential bias, each interviewer selected to perform patient interviews will be experienced in delivering qualitative interviews in similar settings and will also be mindful of possible potential bias when delivering the interview questions, such as refraining from asking leading questions. Each patient will be asked an identical set of questions, which will be void of emotive language and closed questions where possible. Questions have been chosen and approved based upon clinical guidance based upon previous information given by patients with AF who experience bleeds while prescribed anticoagulants.

3.3.1 Patient Reported Outcome (PRO) Measures

An extensive literature search at the outset of study design confirmed that there is currently no known validated Patient Reported Outcome Measure (PROM) which specifically captures impact of bleeding on Quality of Life (QoL). In lieu of having access to such PROM, three previously validated and widely used PROMs will be used to allow for comparisons with larger databanks. The questionnaires that will be completed for the study consist of:

- EQ-5D-5L;
- Perception of Anticoagulant Treatment Questionnaire (PACT-Q); and
- Atrial Fibrillation Effect on QualiTy-of-life (AFEQT).

EQ-5D-5L

The EQ5D has been developed by the EuroQoL group for use in clinical studies as a patient reported outcome measure, commonly used for reporting the current health status of an individual. Patients rate their health from 1 to 5 based on 5 components: mobility, self-care, usual activities, pain/discomfort, and anxiety/depression. A 5-digit number will be generated (e.g. 11111), giving an indication of the patients' current health status. The 5L version of EQ5D has been selected for use in this study as it is considered to

have improved sensitivity compared with the 3L version when capturing quality of life issues in patients living with different health conditions³⁴. The 5L version has also been accepted for use in previous studies investigating quality of life in patients with atrial fibrillation taking oral anticoagulants³⁵.

As part of the EQ5D assessment, patients will also indicate pain levels using a visual analogue scale (VAS) which asks the patient to place a cross over a graduated line from 0 (no pain) to 100 (worst pain imaginable).

PACT-Q

PACT-Q is a two-part PROM, which is used in AF studies to capture patients' perception of treatments before and after initiation. The questionnaire comprises of 7 items for Part 1 (treatment expectations) and 20 items in Part 2 (convenience, burden of disease and treatment, anticoagulant treatment satisfaction, taking an average of 20 minutes total to complete (10 minutes per section). Patients are asked to mark answers on a Likert scale from 1 to 5. For the purpose of this study, only Part 2 will be completed by all patients.

AFEQT

The AFEQT is a self-reported measure which directly measures impact of atrial fibrillation (AF) on quality of life. The aspects of quality of life aspects covered in the questionnaire detail impact of AF on hobbies, relationships, activities including walking or sports, mental health, and side effects from treatment (including side effects such as nosebleeds, bleeding gums, heavy bleeding from cuts and bruising), over the last 4 weeks prior to point of completion. Patients will answer each question on a Likert scale from 1-7. The AFEQT consists of 20 items in total.

3.4 Definitions of Study Variables

As defined by the International Society for Thrombosis and Haemostasis^{2 32} for non-surgical patients

Major bleed

1. Symptomatic bleeding in a critical area or organ, such as intracranial, intraspinal, intraocular, retroperitoneal, intraarticular, or pericardial, or intramuscular with compartment syndrome.

2. Bleeding causing a fall in hemoglobin level of 2 g/dL (1.24 mmol/L) or more, or leading to transfusion of two or more units of whole blood or red cells.

Minor bleed

All non-major bleeds will be considered minor bleeds. Minor bleeds will be further divided into those that are clinically relevant and those that are not. Some examples of minor bleeds include but not limited to:

- Nose bleeds
- Bloody stools
- Small, manageable cuts (e.g shaving cuts)
- Noticeable and/or persistent bruising

Clinically Relevant Minor Bleed

A clinically relevant minor bleed is an acute or subacute clinically overt bleed that does not meet the criteria for a major bleed but prompts a clinical response, in that it leads to at least one of the following:

- A hospital admission or attendance at A&E for bleeding, or
- A physician guided medical or surgical treatment for bleeding, or
- A change in antithrombotic therapy (including interruption or discontinuation of oral anticoagulant).

Other variables collected in the study will be the following:

- Recruitment pathway
- Medication type
- Co-morbidity/ies, if present
- Location of bleed
- Impact of COVID-19 pandemic and resulting restrictions and closures on ability to seek medical care for a bleed

Collecting the above confounding variables, each of which also has the potential to have some impact on QoL for patients with AF who experience bleeding (while anticoagulated), will allow researchers to reflect on and account for any resulting confounder bias. Confounding variables will be reported on within the end of study descriptive analysis.

3.4.1 *Outcomes/Endpoint Variables*

Quality of life data and the impact of the anticoagulation treatment will be collected via validated patient-reported outcome measures (PROMs). We will also include a small number of additional relevant questions regarding when the bleed occurred, the nature of the bleed and their current treatment. We will also collect the documented cause and location of bleed as identified in discharge summary (for secondary care) in patients with major bleeds.

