A cross-sectional, observational feasibility study which will provide a descriptive evaluation of the quality of life (QoL) of atrial fibrillation (AF) patients experiencing a bleed, both in primary care and hospital settings (wards and emergency department (ED)). No control patients (i.e. no-bleed patients) will be enrolled as part of this feasibility phase.

Objective(s):

Primary objective

- To test the feasibility of identifying patients with both minor and major bleeds as a result of anticoagulant treatment for AF and evaluating their QoL through both primary and secondary care settings.

Secondary Objectives

- To describe and interpret the observed differences in QoL by type of bleed.
- To describe the treatment received and the nature of the bleed experienced by the patient.
- To undertake structured qualitative interviews to gain detailed insight into issues from a patient perspective, for those who live with AF and have experienced a recent bleed while taking anticoagulants.
- To observe appropriateness of three chosen PROMs (EQ5D, AFEQT and PACT-Q, part 2) in capturing QoL data, specifically post a bleeding event for AF patients who are taking anticoagulants.

Outcome measure(s):

Primary outcome measures

- The study will be considered feasible if recruitment efforts prove successful:
 - A sample size of 50-80 patients will be required for the study in line with the guidance outlined in the Lancaster et al (2004) publication regarding feasibility studies¹. A minimum of 50 patients recruited will deem the study as successful.

- Patient reported outcome measures (PROMs) will be used in the study using a survey design to collect QoL data from patients directly in both primary and secondary care settings. Three validated questionnaires will be used in this study: EQ5D, AFEQT and PACT-Q. All questionnaires have previously been used in atrial fibrillation studies to collect QoL data.

Secondary outcome measures

- Patients will be asked to provide their anticoagulant medication information along with full details of the bleed they have experienced, which will be used to later categorise the bleeds as minor or major by a medical professional, during the data cleaning and analysis. Medication and bleed details will be recorded before each patient completes the selected study PROMs.

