2.2 Secondary Objectives

- To describe and interpret the observed differences in QoL by type of bleed.
- To describe the treatment received and the nature of the bleed experienced by the patient.
- To undertake structured qualitative interviews to gain detailed insight into issues from a patient perspective, for those who live with AF and have experienced a recent bleed while taking anticoagulants.
- To observe appropriateness of three chosen PROMs (EQ5D, AFEQT and PACT-Q, part 2) in capturing QoL data, specifically post a bleeding event for AF patients who are taking anticoagulants.

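### The plan names no source for the haemoglobin fall in major-bleed criterion 2, and its one record extraction is limited to bleeds already called major

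*Protocol*

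**What the plan says.** Protocol section 3.4 gives two routes to a major bleed. The first is symptomatic bleeding at a critical site. The second is worded as follows: "Bleeding causing a fall in hemoglobin level of 2 g/dL (1.24 mmol/L) or more, or leading to transfusion of two or more units". Everything else falls into the other class: "All non-major bleeds will be considered minor bleeds".

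The input to the classification is described in the Synopsis, under secondary outcome measures: "Patients will be asked to provide their anticoagulant medication information along with full details of the bleed they have experienced". The same sentence then gives the purpose of these patient-supplied details, and the timing: "which will be used to later categorise the bleeds as minor or major by a medical professional, during the data cleaning and analysis". Section 3.3 (Outcomes) agrees: "Patient reported bleeds will be posthumously classified into minor or major bleeds by a clinician", where the adverb evidently means afterwards.

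Sections 3.3 and 3.4.1 name the bleed data. There are "additional relevant questions regarding when the bleed occurred, the nature of the bleed and their current treatment", and then one extraction from records: "We will also collect the documented cause and location of bleed as identified in discharge summary (for secondary care) in patients with major bleeds". Section 2.2 adds an objective that bears on the same data: "To describe the treatment received and the nature of the bleed experienced by the patient".

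**The concern.** A haemoglobin fall is a laboratory result. It can be established from a record but seldom from a patient's account. The plan bases classification on the patient's account. It uses the discharge summary only for two other items, and only in patients whose bleed is already taken to be major. The record that could show a bleed to be major on criterion 2 is therefore not planned to be read for that purpose, and for bleeds not yet called major it is not planned to be read at all.

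This is not a remote corner of the definition. Section 1.1 lists intracranial, gastrointestinal, genitourinary and respiratory tract bleeding as complications of anticoagulation. Of these, only intracranial bleeding is among the sites that criterion 1 names, although that list is illustrative. For the others, criterion 2 is the evident route to the major class.

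At stake is the grouping variable of the descriptive results. Bleed type divides patients for the secondary objective on QoL by type of bleed (section 2.2) and for the comparison of anticoagulant with bleed type (section 4). It also determines how many major bleeds the study can say it identified and recruited, which is part of the primary objective in section 2.1.

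**Working it through.** The protocol gives no figure to reproduce. The check sets what the definition needs beside what the plan says it will obtain.

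**1. Inputs that criterion 2 needs (section 3.4).** Either a haemoglobin fall of at least 2 g/dL or the number of units transfused. Outside the definition, the protocol mentions neither haemoglobin nor transfusion.

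**2. What the patient supplies (Synopsis; sections 2.2, 3.1, 3.3 and 3.4.1).** Timing and nature of the bleed, current treatment, and full details of the bleed in general terms. The objective on treatment received could bring in a transfusion. Nothing here is likely to yield a haemoglobin fall.

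**3. What the discharge summary supplies (sections 3.3 and 3.4.1).** Cause and location. Location informs criterion 1. Neither item informs criterion 2, even in the patients to whom the extraction applies.

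**4. Order of steps.** The extraction is limited to patients with major bleeds, but the Synopsis places the major/minor decision in data cleaning and analysis. If the limit refers to some provisional label, the protocol does not say who assigns it or from what. On either reading, a hospital bleed not initially thought to be major has no extraction planned.

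**5. Other uses of records.** The searches of GP, ward and ED records in sections 3.1 and 3.3 serve to find patients. The review of medical notes in section 6.4 is sponsor quality control. For patients recruited through online support groups (section 3.1), consent and questionnaires are digital and no record source for the bleed is named.

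**6. Direction.** A bleed that meets criterion 2 on haemoglobin alone would reach the clinician without the fact that makes it major. The definition has no category for bleeds that cannot be assessed, so minor is the likelier label. This is an inference, not a stated rule.

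**7. Size.** The share of major bleeds that qualify on haemoglobin alone is not in the protocol. The following is an illustration under assumptions, not an estimate. Let the true split be equal, which section 3.1 aims for only as far as feasible. Let a share s of true majors be recorded as minor and no minors as major, and let the misplaced majors have the same mean QoL as the other majors. Then:

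- share of the recorded minor group that is truly major = s/(1+s)
- observed major–minor difference as a fraction of the true one = 1/(1+s)

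| Assumed s | s/(1+s) | 1/(1+s) |
|---|---|---|
| 10% | 0.10/1.10 = 9% | 1/1.10 = 91% |
| 25% | 0.25/1.25 = 20% | 1/1.25 = 80% |
| 50% | 0.50/1.50 = 33% | 1/1.50 = 67% |

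These fractions do not depend on the number of patients. They show only that the error, if it occurs, pulls the two groups together.

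**The case against.** The strongest reply is that a protocol need not itemise the case report form, and the form is not shown. The list of further variables in section 3.4 is headed as other variables and then described as confounders, so it was never meant to list classification inputs. The inputs to the clinically relevant minor category are not itemised there either. Full details of the bleed and the treatment received may well cover a transfusion. The discharge-summary sentence can be read as extra description of major bleeds rather than as the source for classifying them. The residual rule concerns bleeds that fail the definition; it does not say that unassessed bleeds are minor, and a clinician makes the judgement.

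Much of this stands. A reader might infer that the study collects neither criterion-2 input. The protocol does not support that: its lists are not exhaustive, and transfusion is plausibly captured. A reader might also infer that every bleed major only on criterion 2 will be counted as minor. That goes too far, for the same reason and because no such rule is written.

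What does not fall away is the stated source and the stated restriction. The plan says that the details used for classification come from the patient, and it limits the one record extraction to cause and location in major bleeds. A fuller form completed by the patient would not supply a haemoglobin fall. An analysis plan could not recover values that were never collected.

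**Conclusion.** The point holds as a minor design weakness. As written, the plan gives no source for the haemoglobin part of criterion 2, and its only named record extraction depends on a class assigned later. Bleeds that are major on haemoglobin alone may be recorded as minor. The number cannot be estimated from the protocol.

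The conclusion rests on two assumptions: that patients rarely know their haemoglobin fall, and that the unseen case report form does not direct staff to obtain it from records. Bleeds that also meet criterion 1, or whose qualifying transfusion the patient reports, are not affected.

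A reader might infer that the feasibility decision is compromised. It is not. Eligibility in section 3.2.1 accepts either class, and the criteria in section 4.1 (50 eligible patients, retention, PROM completion) do not use bleed type. Nor does the monitoring of major and minor numbers in section 3.1 contradict later classification, since counting reported bleeds is compatible with a provisional class. The effect is confined to the descriptive results by bleed type and the reported count of major bleeds.

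**What to change.** In sections 3.3 and 3.4.1, replace the restriction to major bleeds. For every bleed identified in secondary care, extract haemoglobin fall and units transfused from the discharge summary, together with cause and location, and do so before the clinician classifies the bleed.

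For all other patients, including those recruited online, ask whether they were transfused and with how many units. Report how many bleeds could not be assessed on criterion 2, so that they are not silently presented as confirmed minor bleeds. Outside secondary care this makes the gap visible but does not close it: a bleed that is major on haemoglobin alone would still go unrecognised there.

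The bleed definition, including its residual rule, stays unchanged.

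The cost is a wording change, two extraction fields and a short patient item. More discharge summaries must be read, some will lack haemoglobin values, and patient-reported units may be inaccurate.

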4 STATISTICAL ANALYSIS

Due to the feasibility aspect of the study and the low number of cases, a full statistical analysis is not planned. A descriptive analysis of QoL reported by AF patients following a minor and/or major bleed, while anticoagulated, will be performed. Patients who experience multiple bleeds over the course of study participation and consequently report these to research staff will be included, and multiple bleeds will be posthumously categorised into minor or major bleeds by a clinical professional and included as part of the descriptive analysis. Recorded treatment type (anticoagulant used) will be compared with type of bleed (minor/major) to determine if there is any possible linkage which could warrant further testing. Comparison to age-adjusted population norms may be insightful but no comparisons with controls are planned for this feasibility assessment.

A brief thematic analysis (Braun and Clarke, 2006)³³ will be conducted on transcribed interview data, to draw out important common themes relating to the study question, which will not be directly captured through the chosen PROMs. Specific qualitative data analysis software, NVivo 12, will be used for additional insight and to identifying trends in unstructured data captured during study interviews.

Lastly, CRF's and online survey links will include sections for eligible patients to provide open-ended feedback regarding each of the PROMs used in this study and how far the PROM captured bleed-specific QoL issues for anticoagulated AF patients. As previously stated, this information will not be used to

conduct a full statistical analysis but will allow researchers to gauge each PROM performance in capturing QoL post-bleed(s) for these patients.

4.1 Progression Criteria

The feasibility of the trial methods, recruitment strategies, and its potential to be further developed and into a full qualitative study will be measured on key progression criteria. These criteria have been approved by our Trial Steering Committee and study managers, where applicable:

- Minimum requirements met for recruitment (50 eligible patients)
- Retention of at least 50% of enrolled patients at follow-up
- 70% PROMs data completion at baseline and 40% completion of PROMs at follow-up

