2 OBJECTIVES

2.1 Primary Objectives

To test the feasibility of i) identifying and recruiting patients with both minor and major bleeds³² as a result of anticoagulant treatment for AF associated events, and ii) measuring their QoL in both primary and secondary care settings.

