The study will aim to enroll all patients who have AF and are anticoagulated, and who have experienced a bleed within a maximum of 30 days at point of enrolment. Patients experiencing bleeds over 30 days prior to enrolment will not be considered for the study at this stage. Numbers of minor and major bleeds reported will be monitored to ensure equal numbers of patients experiencing both types of bleeds are included, as far as feasible. Should an unequal proportion of n numbers occur between type of bleed, patients will not be turned away if they are willing to participate. Researchers will monitor numbers closely and attempt to achieve an equal proportion of minor and major bleed patients. If a balance of major and minor bleeds cannot be achieved within the chosen study population, it will be noted for informing study design of any related future studies.

Patients who meet all study criteria will undertake an informed consent process, where they will be provided with full study details in a patient information sheet (PIS) and asked to sign appropriate documentation to indicate agreement to take part. Patients will have at least 24 hours to deliberate if needed and will have the opportunity to ask any questions before consenting to take part. For surveys which are completed online via a survey link, e-consent will be received according to HRA advice. Patients must agree to provide current contact details for the study team to be kept confidentially by the study team for follow-up purposes. Basic patient demographic information will be collected by qualified research nurses and recorded on case report forms (CRFs), along with details of any bleed(s) experienced. Additional anecdotal questions will be asked relating to ongoing patient management of atrial fibrillation during the current pandemic of Coronavirus, such as the ease of seeking medical care in a situation of a lockdown and social distancing where visits to anticoagulation clinics are limited or entirely stopped. All study documentation will comply with Good Clinical Practice (GCP) guidelines and General Data Protection Regulation (GDPR).

Patient Questionnaires

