3.2 Study Population

Adult patients (≥ 18) who have AF are actively prescribed oral anticoagulant therapies (OATs) and have recently experienced bleeds, up to a maximum of 4 weeks prior to enrolment. No upper age limit will be applied, but patients must match all other inclusion/exclusion criteria (section 3.2.1). Patients will be selected from the Swansea area only, who attend/have attended either anticoagulation clinics within the Swansea City Health Cluster, Morriston emergency department or have been admitted to wards at Morriston Hospital due to a bleed.

3.2.1 *Inclusion Criteria*

- Adult patients (≥ 18 years old)
- Patients who can understand all study information and literature to provide fully informed consent
- Atrial fibrillation (AF) as the primary diagnosis
- Having a major or minor bleed up to a maximum of 30 days prior to point of enrolment
- Receiving oral anticoagulation therapy for AF

3.2.2 *Exclusion Criteria*

- Pregnant women
- Patients with active cancer
- Patients unable to consent for themselves
- Patient on concomitant antiplatelet therapy

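### The recruitment criterion counts any 50 patients, so the study could be declared feasible for both bleed types with no patients of one type enrolled

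*Protocol*

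**What the plan says.** Protocol 2.1 makes the feasibility of "identifying and recruiting patients with both minor and major bleeds" the first part of the primary objective; the synopsis states the same aim.

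The decision rule is in 4.1. Its recruitment criterion is "Minimum requirements met for recruitment (50 eligible patients", with no count by bleed type. The other two criteria are 50% retention, and questionnaire completion of 70% at baseline and 40% at follow-up. Both apply to all enrolled patients together. The synopsis, under primary outcome measures, adds: "A minimum of 50 patients recruited will deem the study as successful".

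Eligibility in 3.2.1 requires "Having a major or minor bleed up to a maximum of 30 days prior to point of enrolment", so either type suffices. Section 3.4 defines minor by exclusion, "All non-major bleeds will be considered minor bleeds", and its examples include "Small, manageable cuts (e.g shaving cuts" and "Noticeable and/or persistent bruising". The same section divides minor bleeds into clinically relevant and other.

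On balance, 3.1 (Screening & Enrolment) says that researchers will watch the two counts and try to keep them equal, and that willing patients are accepted even if they are not. It continues: "If a balance of major and minor bleeds cannot be achieved within the chosen study population, it will be noted", for use in designing later studies. The synopsis describes the expected 50 to 80 patients as stratified by major and minor bleed, but gives no stratum sizes.

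**The concern.** The objective has two parts and the criterion has one. A total of 50 cannot tell whether both kinds of patient were found, because patients of one type can make up for a complete absence of the other. The gap works in both directions: 50 minor-bleed patients meet the criterion, and so do 50 major-bleed patients.

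The criteria in 4.1 decide whether the work is developed further. A pass on a one-sided sample would be read as support for a larger study of both bleed types when recruitment of one had not been shown. It would also leave little or nothing for the secondary objective of describing quality of life by type of bleed.

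This is not a detail left to a statistical analysis plan. The protocol fixes the rule itself.

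**Working it through.** **1. The stated figure.** The 50 is a count attributed to cited feasibility guidance. The protocol attaches no precision target, effect size or power to it, so there is no calculation to reproduce.

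**2. Smallest count of one type that passes every criterion.** Take 50 patients, all with minor bleeds.

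- Recruitment: 50 eligible, met.
- Retention: 0.50 × 50 = 25 patients at follow-up, met if 25 return.
- Questionnaires, counted per patient: 0.70 × 50 = 35 at baseline and 0.40 × 50 = 20 at follow-up, met if that many are complete.

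None of these refers to bleed type, so the smallest number of major bleeds compatible with passing is 0. Exchanging the two types gives the same result for minor bleeds.

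**3. What 0 of 50 would show.** The exact 95% upper limit for the share of major bleeds is 1 − 0.025^(1/50) = 7.1%. Such a sample would pass while indicating that major bleeds are at most about one in 14 of those recruited by these routes.

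**4. Range of outcomes.** The protocol gives no expected share p of major bleeds among recruits, so p is assumed here. The 50% row is the protocol's own equal-numbers aim. The number of major bleeds is taken as Binomial(50, p); expected major = 50p, expected minor = 50(1 − p), and the chance of none = (1 − p)^50.

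| Assumed p | Expected major | Expected minor | P(no major) | P(4 or fewer major) | P(10 or more major) | Recruitment criterion |
|---|---|---|---|---|---|---|
| 5% | 2.5 | 47.5 | 7.7% | 89.6% | <0.1% | met |
| 10% | 5 | 45 | 0.5% | 43.1% | 2.5% | met |
| 20% | 10 | 40 | <0.1% | 1.8% | 55.6% | met |
| 50% | 25 | 25 | <0.1% | <0.1% | >99.9% | met |

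The cut-offs of 4 and 10 only illustrate the spread; the protocol states no minimum per type. The last column is the point: the criterion returns the same answer in every row.

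**5. Do the balancing provisions reach the decision?** Monitoring and the equal-numbers aim (3.1) act on recruitment effort, not on the verdict. The stated consequence of failing to balance is a note for future design. The stratification in the synopsis has no sizes attached. Neither is mentioned in 4.1.

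**The case against.** The strongest reply is that this is a feasibility study and already treats balance sensibly. Counts by type are monitored, equal numbers are sought, a hospital drive runs alongside the primary-care and online routes, and any imbalance is recorded to inform the next study, which is what a feasibility study is for. If the balancing works, the sample looks like the 50% row and the gap never shows. All of this is fair. It lowers the chance of a one-sided sample but does not change what the rule would conclude from one.

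Four stronger readings are tempting, and the protocol does not support them.

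- **Major bleeds are the harder type to find.** Section 5 says the opposite in kind: it names minor-bleed patients as potentially challenging to identify, because they often do not raise the event with a GP. Major bleeds may be scarcer, but the protocol does not say so.
- **A lopsided sample would be hidden.** It would not. Quality of life by bleed type and the nature of the bleed are secondary objectives (2.2), a clinician classifies the bleeds, and recruitment pathway and bleed location are collected (3.4). The mix would be visible in the report. The fault lies in the pass or fail label.
- **Trivial bleeds should not count.** Section 3.4 does admit shaving cuts and bruising, but this is deliberate. Sections 1.1 and 3.1 set out to reach bleeds that patients would not normally report, and 1.2 hypothesises an effect at either severity.
- **Fifty recruits satisfy everything.** They meet the recruitment criterion and the synopsis success rule. Section 4.1 also requires retention and questionnaire completion, though neither depends on bleed type.

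**Conclusion.** The concern holds in a limited form. The decision rule in 4.1 and the matching synopsis statement do not test the objective they serve: a sample with 0 major or 0 minor bleeds could be declared feasible. This follows from the wording alone and rests on no assumed share.

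How likely such a result is cannot be settled from the protocol. The expected 2.5, 5, 10 and 25 major bleeds among 50 follow from assumed shares of 5%, 10%, 20% and 50%. A single binomial share also ignores active balancing across recruitment routes. A reader might infer that a shortage of major bleeds is probable; the document does not show that. The rule should be changed because it could give a wrong feasibility conclusion and correcting it is cheap.

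**What to change.** In 4.1 and the matching synopsis line, keep the total of 50 and add that recruitment is judged separately for major and minor bleeds, each against a minimum set by the Trial Steering Committee before recruitment starts. No values are proposed here, because the protocol gives no basis for them; the equal-numbers aim would correspond to 25 and 25. Report the count of clinically relevant minor bleeds alongside, without making it a pass condition.

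State the conclusion for each outcome in advance. If both minimums are met, recruitment is feasible for both types. If only one is met, it is feasible for that bleed type only and not shown for the other.

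The change takes a few sentences in 4.1 and an edit to the synopsis. The clinician classification is already planned, so no extra enrolment or data are needed, and nobody need be turned away. The downside is that the study may have to report a less favourable conclusion than a single total of 50 would allow.
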